#### 4.2 Correlates of Risk and Correlates of Protection

We broadly classify the proposed analyses into two related categories: correlates of risk (CoR) and correlates of protection (CoP) analyses. CoR analyses seek to characterize correlations/associations of markers with future risk of the outcome amongst vaccinated individuals in the study cohort. CoP analyses seek to formally characterize causal relationships among vaccination, antibody markers and the study endpoint, and use data from both vaccine and placebo recipients. Table 1 summarizes these objectives and statistical frameworks that are commonly used to these ends.

The advantage of CoR analyses it that it is possible to obtain definitive answers from the phase 3 data sets, that is one can credibly characterize associations between markers and outcome. The advantage of CoP analyses is that the effects being estimated have interpretation directly in terms of how an antibody marker can be used to reliably predict vaccine efficacy (the criterion for use of a non-validated surrogate endpoint for accelerated approval). The disadvantage of CoR analyses are that a CoR may fail to be a CoP, for example due to unmeasured confounding, lack of transitivity where a vaccine effect on an antibody marker occurs in different individuals than clinical vaccine efficacy, or off-target effects (VanderWeele, 2013). The disadvantage of CoP analyses is that statistical inferences rely on causal assumptions that cannot be completely verified from the phase 3 data, such that compelling evidence may require multiple phase 3 trials and external evidence on mechanism of protection (e.g., from adoptive transfer or vaccine challenge trials). Our approach presents results for both CoR and CoP analyses, seeking clear exposition of how to interpret results, the assumptions undergirding the validity of the results, and diagnostics of these assumptions and assessment of robustness of findings to violation of assumptions.

We conjecture that an antibody marker could qualify as a non-validated surrogate endpoint (meeting accelerated approval criteria) based on meeting all three conditions: (1) demonstration of a strong and robust CoR with confounding control; (2) external data supporting functionality and connection to a mechanism of protection; and (3) CoP analyses supporting that the biomarker is likely to be a CoP and not only a CoR. Mechanisms of protection as in (2) may be learned through passive antibody transfer studies and vaccine challenge studies in animals and/or humans.

Table 1: Correlates of Risk (CoRs) and Correlates of Protection (CoPs) Objectives for Day 57 Markers

Objective Type	Objective
CoRs (Risk Prediction	To assess Day 57 markers as CoRs in vaccine
$\mathbf{Modeling})$	recipients
	a. Relative risks of outcome across marker levels
	b. Absolute risk of outcome across marker levels
	c. Machine learning risk prediction for
	multivariable markers
CoP: Correlates of VE	To assess Day 57 markers as correlates of VE in
	vaccine recipients
	a. Principal stratification effect modification analysis
	b. Assesses VE across subgroups of vaccine recipients defined by
	Day 57 marker level in vaccine recipients
CoP: Controlled	To assess Day 57 markers for how assignment
Effects on	to vaccine and a fixed marker value would
Risk and VE	alter risk compared to assignment to placebo
CoP: Stochastic	To assess Day 57 markers for how stochastic
Interventional Effects	shifts in their distribution would
on Risk and VE	alter mean risk and VE (Hejazi et al., $2020$ )
CoP: Mediators of VE	To assess Day 57 markers as mediators of VE
	a. Mechanisms of protection via natural direct and indirect effects
	a. Estimate the proportion of VE mediated by a marker or markers

#### 4.2.1 [With Day 29 markers]

If Day 29 markers are included, then each of the objectives for Day 57 markers is repeated for Day 29 markers. In addition, the multivariable CoR machine learning objective includes models that include both Day 29 and Day 57 markers.

#### 4.3 Synthesis of the Phase 3 Correlates Analyses for Decisions

Establishment of an immunologic biomarker for approval/bridging applications is generally not based on pre-fabricated criteria nor a single type of correlates analysis. Therefore, the goal of the correlates analysis is to generate evidence about correlates from many perspectives, and to synthesize the evidence to support certain decisions. Consequently, we believe there is value in assessing all of the types of correlates presented in Table 1 in each trial, given that the analyses address distinct questions. Obtaining a set of results from multiple distinct approaches that provide complementary and coherent support may increase the rigor and robustness of an evidence package supporting potential use of an antibody marker as a validated surrogate (for traditional approval) or as a non-validated surrogate (for accelerated approval) (Fleming and Powers, 2012); these uses of a biomarker are summarized below. However, the assumptions needed for valid inferences are somewhat different across the methods, and some of these assumptions have testable implications; therefore examination of the assumptions may lead to favoring some methods over others, and affect the synthesis and interpretation of results, and moreover if diagnostics support that some necessary assumptions are infeasible then certain analyses will be canceled, as described below.

Section 16 summarizes the approach to use and interpretation of the set of multiple correlates of protection methods. Furthermore, depending on the number of study endpoints in the vaccine and placebo arms at the time a trial delivers primary results, some of the Day 57 marker correlates types defined in Table 1 will be evaluable at the first correlates analyses, whereas others will not be evaluable until additional evaluable vaccine breakthrough endpoints have been observed.

As detailed in Table 4, some CoR analyses are done after there are at least 25 evaluable vaccine breakthrough cases, which is considered to be a minimal number to achieve worthwhile precision. On the other hand, the most non-parametric/flexible CoR analyses require more cases, as do the CoP analyses in general, given the need to adjust for all potential confounders in order to fully identify the causal effects parameters of interest and the greater challenge in estimation (compared to CoR analysis) posed by the need to deal with missing potential outcomes.

Finally, we note that meta-analysis of multiple VE trials will provide important empirical support for potentially establishing an immunologic surrogate endpoint, which underscores the necessity of standardizing the VE trials (common study endpoints, common labs and immunoassays, common statistical methods and data analysis).

#### 4.4 Additional Objectives Not Covered in this SAP

An additional objective that will be assessed, but will be described in a separate SAP, is to assess antibody markers over time beyond Day 57 through two years post vaccination, to assess "outcome-proximal correlates." While we do not formally develop methods to address this aim in this SAP, here we very briefly outline approaches that may be pursued to address such aims. For example, a CoR analysis might assess longitudinal markers in vaccine recipients through estimation of the hazard ratio of outcome across levels of the current value of the marker modeled via a linear mixed effects model (e.g., Fu and Gilbert, 2017). A CoP analysis might assess longitudinal markers as mediators of VE (mechanisms of protection), for example by assessing the proportion of VE mediated by the longitudinal marker(s) profile (e.g., Zheng and van der Laan, 2017).

To potentially help addressing these aims, antibody markers should be measured at the time of COV-INF and COVID diagnosis. An open question is whether and how these measurements may be used in outcome-proximal correlates analyses, for example by assuming that the observed marker values on or near the day of diagnosis were present on the date of SARS-CoV-2 acquisition. Justification for this assumption for the COVID endpoint would derive from information that COVID tends to occur within only several days of SARS-CoV-2 acquisition, implying insufficient time for the infection to make new antibodies that would complicate the interpretation of the vaccineelicited antibodies. It is possible that this condition could only be verified in a subset of cases, in which case validation-set missing data statistical methods may be fruitful. More validation work will be required before methods would be used treating marker values at diagnosis as present at endpoint diagnosis and caused solely by the vaccine (i.e., not also caused by natural infection). For the COV-INF endpoint it is less feasible / possible to use the COV-INF sampling marker value to infer the marker value at acquisition, given the unknown period of weeks or months that may have elapsed between acquisition and seroconversion.

Outcome-proximal correlates analyses may be especially relevant if Day 57 antibody markers tend to be generally high in vaccine recipients and this fact leads to a failure of the correlates analyses to identify a Day 57 correlate: if antibodies wane over time then the outcome-proximal correlates analyses could be more sensitive to detect a correlate.

Additional objectives that may be addressed with the at-diagnosis samples include: (1) to characterize abnormal responses, possibly relevant for safety signals; and (2) to assess the effect of pre-existing antibodies on the active immune response to infection and disease.

# 5 Applications of Immune Correlates Analyses: Vaccine Approval Pathways and Standards of Evidence

Suppose that one or more phase 3 trials demonstrates beneficial vaccine efficacy against the primary clinical endpoint (e.g., symptomatic infection, i.e. COVID) meeting pre-specified success criteria, and correlates analyses of Day 57 antibody marker data are conducted based on the clinical data and antibody data from the phase 3 trial(s). These correlates analyses, combined with additional data supporting the role of antibody markers as mechanisms of protection or as surrogates of mechanisms of protection, can buttress two potential applications of an antibody marker (Table 2).

Table 2: Two Potential Vaccine Approval Pathways Based on a Day 57 Antibody Marker Endpoint

Traditional	nal If the marker is scientifically well-established to reliably predict vaccine			
Approval vaccine efficacy, then subsequent efficacy trials may use the marker				
	as the primary endpoint			
	a. Same vaccine for different populations			
	b. Possibly new vaccines in the same class for the same or different populati			
Accelerated	If the marker is judged reasonably likely to predict vaccine efficacy but not yet			
Approval	approval scientifically well established, then accelerated approval based on the marker			
	endpoint may be possible (requires verification of beneficial clinical VE in			
	post marketing studies)			
	a. Same vaccine for different populations			
	b. Possibly new vaccines in the same class for the same or different populations			

Fleming and Powers (2012) defined a *validated surrogate* as a marker that is appropriate for use as an outcome measure for traditional approval of a specific class of interventions against a specific disease, when such interventions are deemed safe and have demonstrated strong evidence that risks from offtarget effects are acceptable. They also defined a *non-validated surrogate* as a marker appropriate for use as an outcome measure for accelerated approval as one established to be "reasonably likely to predict clinical benefit" for a specific disease setting and class of interventions. These definitions provide two goalposts for immune correlates analyses of COVID-19 VE trials.

Table 3 summarizes one possible set of requirements for a Day 57 antibody marker to be accepted as a *validated surrogate* for a COVID-19 disease endpoint for use in approving COVID-19 vaccines for specific populations (e.g., SARS-CoV-2 seronegative adults) using Fleming and Power's definition. These potential requirements are conjectures provided for conceptualization purposes, and are not based on COVID-19 regulatory guidance documents.

Requirements (16. Required)	Endpoints and Evidence Bar
1. Strong evidence for CoR and CoP	COVID and VL endpoints: Highly
in vaccine recipients in animal	significant and predictive
and/or human challenge models	and Severe COVID : Point estimates
,	in the right direction
	and COV-INF, ASYMP-COV-INF: No
	countervailing evidence 
2. Strong evidence that the marker	
is a mechanistic CoP or tightly	Study endpoints used
correlated with a mechanistic CoP	in challenge models
(likely deriving from animal challenge	such as subgenomic
studies of vaccines or passively	SARS-CoV-2 RNA
transferred antibodies)	
3. Supportive evidence from natural history	Same endpoints as in Phase 3 trial
studies of CoRs of re-infection in	(COVID, severe COVID,
SARS-CoV-2 infected individuals	ASYMP-COV-INF, COV-INF, VL Dx)
4. Phase 3 trial strong evidence as a	COVID and $\geq 1$ other endpoint:
CoR in vaccine recipients	Highly significant and predictive
-	and Point estimates in the right direction
	for the other endpoints
	Consistent results Day 29, 57 markers
	Require consistent results from multiple trials
5. Phase 3 trial strong supportive evidence	COVID
as CoP, for at least one CoP type,	Point estimates of association/causal parameters
plus point estimates in the right	in the right direction for the other $endpoints^2$
direction for the other CoP types	
(consistency of evidence)	Require consistent results from multiple trials
6. Temporal ordering support for several	
of the above results, e.g., CoRs	
and CoPs are stronger for COVID	COVID , severe COVID ,
occurrence proximal to vaccination	ASYMP-COV-INF, COV-INF, VL Dx
than distal, synchronized with	
pattern of biomarker waning	
7. Additional support from non-vaccine	COVID , severe COVID ,
interventions, e.g., demonstration of	ASYMP-COV-INF, COV-INF, VL Dx
a neutralization CoP for a monoclonal Ab	
 Countervailing evidence could be any obser	vations that provide evidence against a CoP, e.g.,
relative to Bradford-Hill criter	ia (see Section 16).

Table 3: Potential Traditional Approval Requirements for a Day 57 Antibody Marker

Because CoPs can differ by study endpoint Plotkin (2010) and vaccine efficacy can differ by study endpoint, this criterion will not necessarily be important.

A potential goalpost for a *non-validated surrogate* for accelerated approval can be conceptualized as the same as that for traditional approval, with modifications:

- The package of evidence for the seven sources listed in Table 3 may be less stringent quantitatively, and not requiring success on all of the first six categories.
- Source 4 (Phase 3 CoR in vaccine recipients) would need to have strong evidence (highly statistically significant and highly predictive).
- The support for an immune correlate may be more restricted to a given study endpoint.
- It may no longer be required to have replication of results across two or more Phase 3 trials.

It is hypothesized that a single validated assay will yield a validated or nonvalidated surrogate endpoint, e.g., based on binding antibody IgG concentration or serum ID50 or cID80 titer to viruses pseudotyped with the Spike vaccine insert protein (or live SARS-CoV-2). However, the goalposts could potentially also be met by a synthesis biomarker aggregated from measurements from multiple validated assays if this aggregation substantially improves the correlate (e.g., a co-correlate Plotkin (2010); Plotkin and Gilbert (2018)). However, the preferred approach, for parsimony and practical utility, would be to define a correlates of protection as a single biomarker derived from a single assay.

#### 5.0.1 [With Day 29 markers]

If Day 29 markers are included, then a validated surrogate endpoint or non-validated surrogate endpoint could be defined based on either a Day 57 time point or a Day 29 time point, and possibly also requiring both time points integrated into the same biomarker.

#### 6 Timeline/Sequencing of Correlates Analyses

The correlates analyses are initiated by the availability of (a) a data set defined at or after the primary analysis data set triggered by the accrual of a certain number of primary endpoints (typically approximately 150 in U.S. phase 3 studies); and (b) Day 1, 57 antibody marker data from correlateseligible COVID primary endpoint cases from at least 25 baseline negative vaccine recipients. The latter requirement ensures that there are enough endpoint cases to achieve worthwhile precision for CoR analyses. The HVTN 505 trial serves as a precedent where 25 evaluable vaccine recipient cases provided enough data to reasonably characterize correlates of risk for a preventive candidate HIV vaccine (Janes et al., 2017; Fong et al., 2018; Neidich et al., 2019; Gilbert et al., 2020b). In addition, simulation studies show that correlates analyses at 20 endpoints have notably lower precision.

Table 4 shows the minimum number of baseline negative vaccine recipient endpoints evaluable for correlates analyses that are required before conducting the various planned correlates analyses.

Correlates Analysis Type	Number
CoRs (Risk Prediction Modeling)	
a. (Semi)parametric models with strongly parametrized associations:	
Cox, hinge/threshold logistic regression	25
b. Flexible parametric models: Generalized additive model	35
c. Nonparametric thresholds: Donovan et al. $(2019)/$	
van der Laan et al. (2020)	35
d. Superlearner estimated optimal surrogate	35
CoP: Correlates of VE	50
CoP: Controlled VE	50
CoP: Stochastic Interventional VE	50
CoP: Mediators of VE	50

Table 4: Minimum Numbers of Evaluable Endpoints in Baseline Negative Vaccine Recipients toInitiate Correlates Analyses

#### 6.1 Timeline of Statistical Analysis Reports

We summarize the plans for analysis reports over the whole period of the study. When the Day 1, 57 antibody data from the immunogenicity subcohort are available, the first immunogenicity report will be produced. When Day 1, 57 antibody data on COVID cases are also available, the first correlates of risk report will be produced, focusing on Stage 1 data only. When there is enough follow-up to measure antibody markers at the later time points (i.e., Day 209, Day 394, possibly Day 759), additional immunogenicity and correlates reports will be made, including those that assess outcome-proximal correlates of risk and protection based on Stage 2 data. The initial correlates reports will likely only include the symptomatic infection/COVID study endpoint; as data sets become available for the other endpoints the reports will add correlates analyses against the secondary endpoints.

# 7 General Statistical Issues in Immune Correlates Assessment

Throughout this section, we define the asymptomatic infection endpoint as seroconversion without prior occurrence of the COVID endpoint.

# Issue 1: Timing of endpoint definition, accounting for diagnosis at presentation (i.e., date of virological confirmation of symptomatic COVID – COVID diagnosis) or during post-COVID-19 diagnosis follow-up.

- **COV-INF:** Defined at presentation (if COVID endpoint) or at first positive serotest visit, whichever occurs first
- **COVID:** Defined at presentation/virologic confirmation
- Asymptomatic infection: Defined at first positive serotest (without prior COVID endpoint)
- Non-severe COVID: Ascertained by post-COVID diagnosis followup, where the failure time could be defined by the time of resolution of symptoms

• Severe COVID: Occurs at presentation or at any time during post-COVID diagnosis follow-up

At COVID endpoint diagnosis, participants roll over onto a post-diagnosis follow-up track (Figure 2). This is irrelevant for analysis of the first three endpoints listed above, but for the non-severe COVID endpoint and the severe COVID endpoint special considerations are needed for proper correlates analyses. Survival analysis theory typically requires *predictable processes*, such that non-severe COVID and severe COVID would have failure times defined when the classification of the endpoint is known. However, alternatively, the analysis could be simplified by defining the failure time for all three endpoints COVID, severe COVID, and non-severe COVID to be the date of presentation, even though at that time one needs to look into the future to determine whether the COVID endpoint is severe or non-severe. Such an approach could be justified by thinking of the data as a competing risks data structure, where one observes the time to COVID, and each COVID endpoint has an associated binary endpoint "type", severe or non-severe. The analyses will use this simplified approach. A justification of this simplified approach is that severe COVID is a very rare event among vaccine recipients, and it is the fact of having the event that is important, not whether it happened at or 9 days post COVID diagnosis, such that using a more refined failure time would be unlikely to carry additional meaningful information. If greater than 10% of COVID endpoint cases are missing the endpoint type, then methods accounting for missing endpoint types will be used (e.g., Heng et al., 2020).

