#### Issue 3: Coarseness level of the failure time variable

- 1. **COVID:** Event time defined in 'continuous time' on the day of virological confirmation.
- 2. Asymptomatic infection: Event time defined only at fixed infrequent visits (e.g., Month 6, 12, 18, 24).
- 3. **COV-INF:** Event time defined as 'mixed continuous and discrete', equal to the day of virological confirmation (if COVID) and by the first sero-postive visit (if asymptomatic infection).
- 4. Non-severe COVID: Event time may be defined in continuous time, as the number of days from enrollment to COVID diagnosis plus the number of additional days until the COVID event is known to be non-severe. However, following the decision made for Issue 1, we simplify and define the event time at COVID diagnosis.
- 5. Severe COVID: Event time may be defined in continuous time, as the number of days from enrollment to COVID diagnosis plus the number

of additional days until the COVID event is known to be severe (which may be zero days). However, following the decision made for Issue 1, we simplify and define the event time at COVID diagnosis.

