#### 12.3.5 Univariable CoR: Marginalized Cox modeling for an outcome subject to competing risks (e.g. asymptomatic infection)

If the outcome under study is subject to competing risks, then the Cox model is fit in the same way, except counting the competing risk as right-censoring. Now the parameter being estimated is the marginal conditional cumulative incidence function  $risk_1(t, 1|s) = E_X[P(T \le t, J = 1|s, X, A = 1)]$  where J = 1 is the outcome of interest. To estimate this parameter, we use the fact that the cause *j*-specific hazard  $\lambda_{j1}(t|s, x)$  is linked to the conditional cumulative incidence  $F_{j1}(t|s, x) = P(T \le t, J = j|s, x, A = 1)$  via the formula

$$F_{j1}(t|s,x) = \int_0^t \lambda_{j1}(u|s,x) S_1(u|s,x)$$

where  $S_1$  is the all-cause/overall conditional survival function for the first event of asymptomatic infection or COVID-19, whichever occurs first (i.e., the COV-INF endpoint). Therefore, after fitting the cause J = 1 Cox model, for any fixed t the above formula provides fitted values  $\hat{F}_{j1}(t|s, X_i)$  for each participant i, and then the G-computation estimator of  $risk_1(t, 1|s)$  is

$$\widehat{risk}_1(t,1|s) = \frac{1}{n} \sum_{i=1}^n \hat{F}_{j1}(t|s,X_i).$$

As for the analyses without competing risks, the bootstrap is used for calculating 95% confidence intervals and for testing  $H_0: risk_1(t_F, 1|s) = risk_1(t_F, 1)$ for all s.

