#### В

Clinical Endpoint	Definition
SARS-CoV-2 infection	Positive RNA PCR test or SARS-CoV-2 seroconversion*, whichever occurs first
COVID (Symptomatic infection)	Meeting a protocol-specified list of COVID-19 symptoms with virological confirmation of SARS-CoV-2 infection (symptom triggered)
Asymptomatic infection	SARS-CoV-2 seroconversion* without prior diagnosis of the COVID endpoint ¶
Severe COVID	COVID endpoint with at least one protocol-specified severe disease event
Non-severe COVID	COVID endpoint with zero protocol-specified severe disease events

\*Seroconversion is assessed via a validated assay that distinguishes natural vs vaccine-induced SARS-CoV-2 antibodies

¶Alternatively, the asymptomatic infection endpoint can also include an RNA PCR+ test result obtained through testing regardless of symptoms (e.g., as a requirement for travel, return to school or work, or elective medical procedures) and follow-up to confirm the participant remains asymptomatic

Figure 1: A) Structural relationships among study endpoints in a COVID-19 vaccine efficacy trial (Mehrotra et al., 2020).. B) Study endpoint definitions.

Figure 2: Example at-COVID diagnosis and post-COVID diagnosis disease severity and virologic sampling schedule, in a setting where frequent follow-up of confirmed cases can be assured. Participants diagnosed with virologically-confirmed symptomatic SARS-CoV-2 infection (COVID) enter a post-diagnosis sampling schedule to monitor viral load and COVID-related symptoms (types, severity levels, and durations).

Figure 3: Case-cohort sampling design (Prentice, 1986) that measures Day 1, 57 antibody markers in all participants selected into the subcohort and in all COVID and COV-INF cases occurring outside of the subcohort.

\* These ≥ 25 cases must have available Day 1, Day 57 antibody marker data and be baseline SARS-CoV-2 negative.
 ¶ bAb and nAb data are measured in all cases, regardless of baseline status.
 ‡ And also potentially of some shorter-term secondary endpoints.

Case-cohort Immunogenicity Analysis Set (ccIAS)

NAAT = nucleic acid amplification test; PCR = polymerase chain reaction; bAb = binding antibody; nAb = neutralizing antibody.

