## 25 Appendix: Notes on Planning for Stage 2 Correlates Analyses

The paper Sun, Zhou, Gilbert (submitted) "Analysis of Cox model with Longitudinal Covariates with Measurement Errors and Partly Interval-Censored Failure Time, with Application to an AIDS Clinical Trial" may be a suitable method for assessing antibody markers over time as correlates of the SARS-CoV-2 infection endpoint, once there is follow-up data for more than a year with antibody markers measured at all time points up to at least a year. The paper extends Fu and Gilbert (2017) from right-censored failure time data to partly interval-censored failure time data, which means a composite endpoint is analyzed with one component subject to right-censoring and the other component subject to interval censoring. In our application, the COVID primary endpoint is subject to right-censoring, and seroconversion is subject to interval-censoring.

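### Figure 1B counts any positive RNA PCR as a SARS-CoV-2 infection (COV-INF) event, but Section 7 dates COV-INF only at a COVID endpoint or a positive serology visit.

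*Combined protocol and SAP*

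**What the plan says.** Section 3.2 sends the reader to Figure 1 for the endpoint definitions. The table in Figure 1B defines SARS-CoV-2 infection as "Positive RNA PCR test or SARS-CoV-2 seroconversion*, whichever occurs first". The COVID endpoint in the same table requires more than a positive test: "Meeting a protocol-specified list of COVID-19 symptoms with virological confirmation of SARS-CoV-2 infection (symptom triggered".

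Section 7 sets the timing. Issue 1 says of COV-INF: "Defined at presentation (if COVID endpoint) or at first positive serotest visit, whichever occurs first". Issue 3 repeats the two routes, with the event time "equal to the day of virological confirmation (if COVID) and by the first sero-postive visit (if asymptomatic infection". For the serology route, the same list gives the asymptomatic infection timing as "Event time defined only at fixed infrequent visits (e.g., Month 6, 12, 18, 24".

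Two later places use the same two components. Section 12.3.5 defines its overall survival function "for the first event of asymptomatic infection or COVID-19, whichever occurs first (i.e., the COV-INF endpoint". Section 25 treats the infection endpoint as a composite in which "the COVID primary endpoint is subject to right-censoring, and seroconversion is subject to interval-censoring".

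A footnote to Figure 1B allows, as an alternative, that asymptomatic infection may also include a positive PCR from testing done regardless of symptoms, with follow-up confirming that the participant stays asymptomatic. Section 7 does not take up this option.

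**The concern.** A positive PCR without the COVID endpoint has a place in the Figure 1B definition and none in the Section 7 date rule. The Figure 1B footnote shows that such results are foreseen, naming tests for travel, school, work and elective procedures. Two programmers working from different pages would build different COV-INF case lists and different event times.

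Section 3.2 lists COV-INF among the endpoints that may be assessable at or shortly after the first correlates analysis. Under Figure 3, Day 1 and Day 57 markers are measured in all COV-INF cases outside the subcohort. Section 8.2.1 gives diagnosis-date samples from COV-INF cases the highest assay priority. The definition therefore also bears on who is assayed and which sample counts as the diagnosis sample.

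**Working it through.** **Step 1: follow one participant through both rules.** The participant is PCR positive, does not meet the COVID symptom list, and is otherwise eligible.

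| Situation | Figure 1B | Section 7, Issues 1 and 3 |
|---|---|---|
| Positive PCR, later seroconverts at a usable visit | Case on the PCR date | Case on the serology visit date |
| Positive PCR, data cut or unblinding before the next positive serology | Case on the PCR date | Not a case |
| Positive PCR, never seroconverts, never meets COVID | Case on the PCR date | Not a case |

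The second row follows because Section 3.2 uses no post-unblinding follow-up.

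**Step 2: size of the dating gap.** The SAP states no COV-INF event count, so there is no figure of its own to reproduce. The gap can be illustrated from its visit schedules.

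Inputs from the SAP:
- Counting starts 7 days after Day 57 (Section 3.2), so at Day 57 + 7 = 64.
- Serology is at Months 6, 12, 18 and 24 (Issue 3, given as an example). At 30.44 days per month the gaps are about 182.6 days and Month 6 is Day 182.6.
- As an alternative schedule, the later sampling days are 209, 394 and 759 (Section 4.1).

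Assumptions of this review: months run from enrolment, infection times are uniform from Day 64 to the last visit, the PCR falls at infection, and serology turns positive after a lag of 0 to 28 days. The SAP gives no lag.

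With zero lag, the mean delay is the sum of squared gaps divided by twice the total time:
- Month schedule: first gap 182.6 − 64 = 118.6, then three gaps of 182.6. (118.6² + 3 × 182.6²) / (2 × 666.5) ≈ 86 days.
- Day schedule: gaps 145, 185 and 365. (145² + 185² + 365²) / (2 × 695) = 188,475 / 1,390 ≈ 136 days.

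| Schedule | Mean delay, lag 0 to 28 | Maximum, lag 0 to 28 | Delayed more than 30 days |
|---|---|---|---|
| Months 6/12/18/24 | 86 to 113 days | 183 to 211 days | 82% to 99% |
| Days 209/394/759 | 136 to 164 days | 365 to 393 days | 87% to 99% |

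These describe infections that some later visit picks up. Under the Figure 1B rule the delay is 0.

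**Step 3: share missed at an early cut.** For illustration, take the simulation default in Section 24.3.1 of 180 days after Day 57, so follow-up ends at Day 237. The window is 237 − 64 = 173 days, with infections uniform over it. An infection is missed if it falls after the last usable visit minus the lag.
- Month 6 visit: (237 − 182.6) / 173 = 31% at lag 0; (237 − 154.6) / 173 = 48% at lag 28.
- Day 209 visit: 28 / 173 = 16% at lag 0; 56 / 173 = 32% at lag 28.

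These are shares of PCR-positive, non-COVID infections, not of all COV-INF cases. Participants who never seroconvert are missed at any horizon. If the cut precedes a participant's first post-Day 57 serology visit, every such infection before it is missed.

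**The case against.** The strongest reply is that Figure 1B is the outlier. Issues 1 and 3, Section 12.3.5 and Section 25 all use the same two components, so Section 7 could be read as the working rule and Figure 1B as a conceptual table. That reading is possible, but Section 3.2 names Figure 1 as the place where the endpoints are defined, and nothing in the SAP ranks the two.

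A second reply is that detail for secondary endpoints is deferred. Section 12 opens by saying the plan focuses on COVID and will be extended later, Section 6.1 expects initial reports to cover COVID only, and the Prelude calls the SAP a work in progress. This lowers the urgency. It does not remove the conflict, because Section 7 already fixes a COV-INF date rule.

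A third reply is that no passage shows how many PCR-positive, non-COVID participants there will be, or that people with symptoms short of the list are swabbed during the counted follow-up. That stands, and materiality cannot be established from the SAP. Nor should the point lean on the evidence bar in Table 3, whose requirements Section 5 describes as conjectural.

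**Conclusion.** The inconsistency is real and sits in the current text. Followed as written, Section 7 dates a PCR-positive, non-COVID infection at a later serology visit or does not count it, while Figure 1B counts it on the PCR date. On the Month 6/12/18/24 example the date differs by up to about 6 months, and by more if seroconversion lags. The averages and missed shares above rest on uniform infection times, an assumed lag of 0 to 28 days and, for the missed shares, an illustrative cut. The point concerns a secondary endpoint and an unknown number of participants.

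Three stronger readings are tempting, and the SAP does not support them.
- A reader might infer that the competing-risks estimator in Section 12.3.5 is internally wrong. It is not on this ground: its overall survival function is defined as the first of asymptomatic infection or COVID, so it matches its two components. Only the label equating that event with COV-INF conflicts with Figure 1B.
- A reader might infer that the mismatch causes people with symptoms short of the list to be called asymptomatic. Section 7 and the main entry in Figure 1B define asymptomatic infection in the same way, as seroconversion without a prior COVID endpoint. That is a stated operational choice, not a product of this conflict.
- A reader might infer that the Figure 1B footnote requires confirmed absence of symptoms for every asymptomatic case. It is an optional alternative, and the confirmation attaches to its added PCR route.

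**What to change.** - In Section 7, Issues 1 and 3, date COV-INF at the first of a positive RNA PCR (with or without the COVID endpoint) or the first positive serology visit, as in Figure 1B.
- In Section 12.3.5, delete the parenthetical equating the first of asymptomatic infection or COVID with COV-INF. The overall survival function itself stays as it is.
- In Section 25, align the components, so that a positive PCR without COVID enters as an event with a known date and is not left to the interval-censored serology part.
- State whether the optional PCR route in the Figure 1B footnote is adopted for asymptomatic infection. The Section 12.3.5 deletion is needed either way, because a positive PCR with symptoms short of the list would still be in COV-INF and not, on that date, in either component.

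The asymptomatic infection endpoint need not be replaced by a new composite. That would change an endpoint to settle a wording conflict.

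The cost is SAP wording and endpoint derivation code, plus a check of which PCR results the analysis data set holds. The downside is that PCR dates from testing outside study visits are unevenly ascertained across participants, so COV-INF event times would mix incidental PCR dates with scheduled serology dates. The SAP should say so when COV-INF results are reported.
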